2.4 Study Objectives

2.4.1 Primary Objective

The primary objective of this trial is to evaluate the efficacy and safety of orally administered nevanimibe hydrochloride (HCl) for the treatment of classic congenital adrenal hyperplasia (CAH).

2.4.2 Secondary Objectives

The following secondary objectives have been defined for this study:

- Assessment of changes in adrenal cortical steroids and steroid intermediates
- Determination of pharmacokinetic (PK) parameters of nevanimibe and its major metabolite(s)
- Assessment of PK/pharmacodynamic (PD) relationships of nevanimibe and its major metabolite(s).

2.5 Study Hypothesis

The hypotheses to be investigated by this study include whether sustained, continuous dosing of nevanimibe HCl will result in greater efficacy than observed in the previous Phase 2 CAH study (ATR-101-201) and whether higher doses are needed. Additionally, it will be evaluated whether the higher doses used in this study still have a sufficient safety profile. The primary efficacy endpoint will be evaluated by means of the percentage of subjects achieving predose serum 17-OHP targets as follows:

- Men and postmenopausal women: 17-OHP $\leq 2 \times$ ULN
- Premenopausal women in follicular phase: 17-OHP $\leq 2 \times$ follicular phase ULN
- Premenopausal women in luteal phase: 17-OHP $\leq (2 \times \text{follicular phase ULN} + (\text{luteal phase ULN} - \text{follicular phase ULN}))$

The responder rate (percentage of subjects achieving the predose serum 17-OHP targets) for Cohort i ($i=1, 2$) will be calculated as follows:

$$\text{Responder rate}_{Ci} = \frac{\text{Number of responders in } Ci}{N_{Ci}} \times 100\%$$

with Ci being the corresponding cohort. The responder rate will also be calculated overall.

The study will be considered positive if 40% or more of enrolled subjects in either cohort were classified as responders at any of the four visits T2 (Day 29), T3 (Day 57), T4 (Day 85) or T5 (Day 113; Amendment 2).

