3.2. Rationale for Study Design

The previous Phase 2 CAH study (ATR-101-201) explored nevanimibe HCl doses ranging from 125 mg to 1000 mg BID, with each dose lasting 2 weeks followed by a 2-week placebo washout. Each subject had the opportunity to dose-escalate based on 17-OHP values assessed after each dose level. Eligible subjects had 17-OHP $\geq 4x$ ULN at screening (i.e., similar to Cohort 1). At baseline, the mean 17-OHP was 53x ULN (ranging from 7 to 187x ULN) for the 10 subjects who received nevanimibe HCl. In that study, although robust decreases in 17-OHP with nevanimibe HCl were observed, only two (20%) subjects were able to achieve 17-OHP levels $\leq 2x$ ULN. However, some of the largest percentage decreases in 17-OHP were observed in subjects with the highest baseline 17-OHP values. This finding was entirely consistent with the known mechanism of action for ATR-101, where depletion of the cholesteryl ester pool may require more than 2 weeks in subjects with markedly elevated 17-OHP (a correlation between larger

adrenal size and higher 17-OHP level has been reported in classic CAH subjects). Also, the cholesteryl ester stores may have been partially replenished during the 2-week placebo washout period that followed each ATR-101 dose period. Thus, hypotheses to be tested for this protocol include whether sustained, continuous dosing of nevanimibe HCl will result in greater efficacy and whether higher doses are needed to demonstrate this effect. Consequently, this protocol will evaluate longer periods of dosing at each dose level with an overall duration of 16 weeks, and explore higher doses of nevanimibe HCl (up to 2000 mg BID). Dosing will commence with nevanimibe HCl at 500 mg BID for 4 weeks prior to up-titrating to the 1000 mg BID dose, as the nevanimibe HCl 500 mg BID dose was well-tolerated in both the previous Phase 2 CAH study and in a previous drug-drug interaction study, and experience from previous studies suggests that study drug tolerability is improved by longer dosing.

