Use of nevanimibe HCl in Cohort 2 is designed to demonstrate sustained decreases 17-OHP to a target value of $\leq 2x$ ULN while the subject receives glucocorticoid doses that are lower than their doses at screening. Although subjects in Cohort 2 have 17-OHP values at or very close to goal at screening (i.e., $< 4x$ ULN), this comes at the “cost” of suppressive glucocorticoid doses and associated side effects. In this cohort, the temporary, purposeful rise in 17-OHP associated with a decrease in glucocorticoid dose toward non-suppressive levels (see Appendix 2) creates the potential for nevanimibe HCl to demonstrate a truly novel clinical therapy. Nevanimibe HCl could potentially create the optimal/ideal clinical situation that does not currently exist for classic CAH patients, i.e., control of 17-OHP with non-suppressive glucocorticoid doses. Ultimately, in a future study, a similar outcome to that of Cohort 1 could be demonstrated in Cohort 2 with a longer duration of treatment (i.e., the glucocorticoid dose could be decreased once the 17-OHP has reached the target level).

The dose range for this study is supported by the previous CAH Phase 2 study, extensive ACC Phase 1 data, and comprehensive non-clinical and *in vitro* studies conducted with nevanimibe HCl (additional information regarding the dose rationale may be found in Appendix 7 and in the ATR-101 (nevanimibe HCl) Investigator's Brochure).

The ACC Phase 1 study provides tremendous reassurance for the safety of the doses proposed, since both the dose levels and the duration of treatment have already far surpassed those being proposed in this protocol. The highest dose evaluated in the ACC study was 158.5 mg/kg/day, which is approximately 3x the highest dose proposed for this protocol for a 75-kg subject. In addition, the average duration of exposure was 58 days across the 14 nevanimibe HCl dose cohorts, with several subjects having received nevanimibe HCl for as long as 5 to 12 months at doses > 2000 mg BID. Nevanimibe HCl was extremely well tolerated in the ACC study population, which is markedly less robust (all had advanced stage cancer and most had undergone multiple prior treatment regimens) relative to the classic CAH patient population.

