4.2. Inclusion Criteria

Each subject must meet all the following criteria to be enrolled in this study:

1. Provision of signed and dated informed consent prior to any study-specific procedures
2. Men and women 18 to 80 (70 in the Czech Republic) years of age (inclusive) at the time of informed consent
3. Documented historical diagnosis of classic CAH due to 21-hydroxylase deficiency based on either or both of the following criteria:
 - Documented genetic mutation in the CYP21A2 enzyme consistent with a diagnosis of classic CAH
 - Historical documentation of elevated 17-OHP (e.g., in infancy or following a cosyntropin/ACTH stimulation test)
4. Serum 17-OHP \geq 4x ULN during the Baseline Period
 - Premenopausal women in the follicular phase of the menstrual cycle must have serum 17-OHP \geq 4x follicular phase ULN
 - Premenopausal women in the luteal phase of the menstrual cycle must have serum 17-OHP \geq (4x follicular phase ULN + (luteal phase ULN – follicular phase ULN))
5. Chronic glucocorticoid replacement therapy for at least 6 consecutive months prior to Screening
6. Stable glucocorticoid and mineralocorticoid regimen for at least 4 weeks prior to the Screening (S1), Baseline (B1), and Enrollment (T1) Visits
7. For subjects who undergo maintenance glucocorticoid dose adjustment between Screening and Enrollment, stable serum 17-OHP levels (adjusted as needed for menstrual cycle phase) prior to Enrollment, defined as the most recent 2 values being within 30% of each other (calculated as $100 \times (1 - (\text{smaller value}/\text{larger value}))$)
8. Female subjects of childbearing potential must consent to use two medically acceptable methods of contraception, excluding depot progesterone, throughout the study period and for 30 days after the last dose of study treatment during any sexual intercourse with a fertile male partner (in France: Fertile subjects (male and female) must consent to use two medically acceptable methods of contraception, excluding depot progesterone, throughout the study period and for 30 days after the last dose of study treatment during any sexual intercourse with a fertile partner of the opposite sex)

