2.7 Randomization and Stratification

No randomization or stratification is performed in this trial. Patients will be allocated to one of two cohorts (Cohort 1 or Cohort 2) according to their screening 17-OHP value. Eligible subjects with a 17-OHP value $\geq 4 \times$ ULN at the initial screening visit will be enrolled into Cohort 1, while patients with a 17-OHP value $< 4 \times$ ULN at the initial screening visit will be enrolled into Cohort 2 if their glucocorticoid (GC) dose can be reduced and a subsequent 17-OHP measurement after GC dose reduction indicates an increase in 17-OHP to $\geq 4 \times$ ULN.

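### A higher responder rate than in ATR-101-201, above all in Cohort 2, would not by itself show greater efficacy, because the target is absolute and Cohort 2 has no counterpart in that study

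*SAP*

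**What the plan says.** SAP 2.5 poses the question of whether continuous dosing "will result in greater efficacy than observed in the previous Phase 2 CAH study (ATR-101-201"). The only efficacy measure it then names is the percentage of subjects reaching a fixed predose 17-OHP target (2x ULN or less, adjusted for cycle phase). The study is positive if at least 40% in either cohort respond at any post-baseline treatment visit, and SAP 7.5 repeats this rule.

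Protocol 3.2 describes the comparator. Its subjects had 17-OHP of at least 4x ULN at screening ("i.e., similar to Cohort 1"). It also reports: "At baseline, the mean 17-OHP was 53x ULN (ranging from 7 to 187x ULN) for the 10 subjects who received nevanimibe HCl". Of these, "only two (20%) subjects were able to achieve 17-OHP levels" of 2x ULN or less.

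Cohort 2 is recruited differently. Protocol 3.2 says that "subjects in Cohort 2 have 17-OHP values at or very close to goal at screening". SAP 2.7 admits them if the glucocorticoid dose can be reduced and a "subsequent 17-OHP measurement after GC dose reduction indicates an increase in 17-OHP to" at least 4x ULN. No upper limit on baseline is set for either cohort, and SAP 2.9 fixes no cohort sizes.

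The responder rate in SAP 7.5 is split by cohort and dose. Baseline fold-ULN is summarised by cohort (SAP 7.4.3), as are absolute and relative change in serum 17-OHP (SAP 7.5 and 7.6).

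**The concern.** With an absolute target, the chance of responding depends on where a subject starts as well as on what the drug does. The hypothesis is framed against a study whose subjects all started at 7x ULN or higher and on average far above that. The success rule lets either cohort make the study positive, and nothing in SAP 2.5 says that only Cohort 1 resembles the earlier population. A positive Cohort 2 could therefore be read as showing that continuous or higher dosing beats the earlier 20%, even if the percentage fall in 17-OHP were the same or smaller.

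**Working it through.** **Inputs from the documents.** Target 2x ULN; entry threshold 4x ULN; earlier baselines 7 to 187x ULN, mean 53x, n = 10, two responders (Protocol 3.2 and 4.2; SAP 2.5 and 7.5).

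**1. The plan's own figure.** 2/10 = 20%, which reproduces. The exact 90% interval is 3.7% to 50.7%, so the 40% bar lies inside the uncertainty of the historical rate.

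**2. Fall needed to reach the target**, 1 − 2/baseline:

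| Baseline (x ULN) | Calculation | Fall needed |
|---|---|---|
| 4 | 1 − 2/4 | 50.0% |
| 7 (earlier minimum) | 1 − 2/7 | 71.4% |
| 53 (earlier mean) | 1 − 2/53 | 96.2% |
| 187 (earlier maximum) | 1 − 2/187 | 98.9% |

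This applies to men, postmenopausal women and follicular-phase women. In the luteal phase, let F be the follicular ULN and d the luteal minus the follicular ULN. Entry is then 4F + d and the target is 2F + d, so the fall needed at the threshold is 2F/(4F + d), which is below 50% when d > 0. The documents give no ULN values, so this cannot be sized further.

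**3. Could Cohort 1 start lower than the earlier study?** The entry threshold is the same, so only chance or recruitment could bring this about. None of the ten earlier subjects was below 7x. If they are treated as a random sample of such patients, the one-sided 95% upper bound for the share between 4x and 7x is 1 − 0.05^(1/10) = 26%.

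**4. Illustration (assumed values, not from the documents).** Each visit's log ratio to baseline is a subject effect, normal with mean ln(1 − median fall) and SD 0.5 or 0.8, plus independent visit noise with SD 0.2 or 0.4. A subject responds if any of four visits is at or below 2x ULN. The ranges cover the four SD combinations.

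| Median fall | From 4x | From 7x | From 53x |
|---|---|---|---|
| 30% | 40–55% | 9–28% | 0.2% or less |
| 50% | 60–76% | 25–43% | 0.5% or less |
| 70% | 81–95% | 58–74% | 2.5% or less |

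In every one of the four SD settings, a 30% median fall from 4x gives a higher responder rate than a 50% fall from 7x: 40.0 against 24.9%, 55.0 against 39.7%, 43.6 against 33.0%, and 53.4 against 43.1%. A weaker effect can thus produce a higher rate.

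**5. What the planned outputs connect.** Baseline fold-ULN and relative change are each summarised by cohort. Neither is set against responder status, and neither is tied to the comparison with ATR-101-201.

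**The case against.** The strongest counter-argument is that the earlier study had the same threshold of 4x ULN. A reader might infer from the 7 to 187x range that the present trial has easier entry. For Cohort 1 the documents do not support that: an entry rule would be set against a realised range. This objection stands in full.

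A reader might also infer that Cohort 2 must enter just above 4x ULN. The stepwise glucocorticoid reduction, with further reductions described only while 17-OHP is below 4x (Protocol 7.1.4 and 7.2.2), makes that plausible. But no upper limit is set and no document gives the resulting distribution, so it remains an inference.

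A simple model with an identical 50% fall for everyone gives 1 − 0.5^4 = 94% response from 4x. That should not be used as the size of the problem. A 50% fall from 4x lands exactly on the target, so each visit is a coin toss, and Amendment 1 subjects have only three such visits. The table above, with between-subject variation, is more cautious, but it still assumes a constant proportional effect. Protocol 3.2 weakens that assumption by reporting that "some of the largest percentage decreases in 17-OHP were observed in subjects with the highest baseline 17-OHP values". Even so, a fall of 96% is needed from 53x.

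Finally, SAP 2.5 contains no formal test against 20%, SAP 7 calls all summaries exploratory, Protocol 3.2 gives Cohort 2 its own purpose (control on glucocorticoid doses lower than at screening), and baseline and relative change are reported by cohort. These points reduce the risk of misreading. They do not remove it, because the hypothesis names the earlier study, the 40% rule can be met by Cohort 2 alone, and no text says that only Cohort 1 has a benchmark.

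**Conclusion.** The point holds for the interpretation of the historical comparison, not as a fault in the entry criteria. A responder rate above 20% does not by itself show greater efficacy than ATR-101-201. This is clearest in Cohort 2, which has no counterpart there, and possible in Cohort 1 if its realised baselines differ. The firm part is arithmetic: the fall needed runs from 50% at 4x to 71% at 7x and 96% at 53x. The simulated response rates depend on assumed variances and a constant proportional effect, and show direction only. How far Cohort 2 differs in practice depends on its realised baselines, which the documents cannot tell us. The change is worth making because it affects what the trial may conclude and costs almost nothing.

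**What to change.** In SAP 2.5, state that the comparison with ATR-101-201 is made in Cohort 1 only, that Cohort 2 has no historical benchmark, and that a positive result in Cohort 2 alone does not answer that hypothesis.

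In SAP 7.5, add a display by cohort of responder status against each subject's baseline fold-ULN and percentage fall in serum 17-OHP. Add a supportive Cohort 1 responder rate limited to baselines of 7x ULN or more, the earlier study's observed range. Note beside it that 7x is only the minimum of ten values: a group at 7 to 10x would qualify although it needs a fall of 71 to 80% (1 − 2/10 = 80%), against 96% from the earlier mean. The individual display should therefore carry the main weight.

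The cost is a few sentences and one display from data already collected, with no change to eligibility, visits or treatment. The downside is a small group for the historical comparison, since about 20 to 24 subjects are shared between two cohorts of unspecified size.

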2.6 Handling of Screening Failures and Drop-outs

Screening failures will be replaced while subjects who withdraw or are removed from the clinical study after enrollment into the treatment period (i.e., start of dosing with study drug) will be replaced if they do not meet the criteria for being an evaluable subject (8 weeks of continuous dosing with at least one post-baseline serum 17-OHP assessment).

2.7 Randomization and Stratification

No randomization or stratification is performed in this trial. Patients will be allocated to one of two cohorts (Cohort 1 or Cohort 2) according to their screening 17-OHP value. Eligible subjects with a 17-OHP value $\geq 4 \times$ ULN at the initial screening visit will be enrolled into Cohort 1, while patients with a 17-OHP value $< 4 \times$ ULN at the initial screening visit will be enrolled into Cohort 2 if their glucocorticoid (GC) dose can be reduced and a subsequent 17-OHP measurement after GC dose reduction indicates an increase in 17-OHP to $\geq 4 \times$ ULN.

2.8 Blinding

No blinding is performed in this clinical trial.

2.9 Sample Size Calculation

Based on results of the previous Phase 2a study of nevanimibe HCl in classic CAH (ATR-101-201), the sample size of approximately 20-24 subjects is considered to be sufficient for evaluating whether nevanimibe HCl at doses of 500-2000 mg BID has clinically meaningful efficacy in the treatment of classic CAH. No formal sample size calculation was performed. There are no pre-specified recruitment targets for Cohort 1 and Cohort 2.

2.10 Planned Interim or Sequential Analysis

No interim or sequential analysis is planned. However, data for Cohort 1 subjects may be analyzed after completion of the trial by the last Cohort 1 subject, while the analysis of Cohort 2 and overall may be conducted after completion of the trial by the last Cohort 2 subject. This option may be used to account for the longer trial duration of Cohort 2 subjects.

2.11 Handling of Changes to the Planned Analyses

Any deviations from planned analyses, the reasons for such deviations, and all alternative or additional statistical analyses that occur before final database lock will be described in amendments to the SAP. All deviations and/or alterations before final database lock or thereafter will be summarized in the clinical study report.

3. Technical Aspects and Coding Conventions

All programs will be written using SAS version 9.4 or higher. Tables, listings, and figures will be provided in separate documents with separate table of contents. A minimum font size of 8 points will be used for the tables, corresponding to a line size of 140 characters and a page size of 8.5 x 11 inches. For listings, a standard font size of 8 points with the line size and page size as defined above will be used to produce the output in 8.5 x 11-inch page size.

Courier New will be used as font for all tables and listings. In headings, titles, and listings only the first word will be capitalized. Missing data will be represented on patient listings as blank fields. Listings will be sorted by subject number unless specified otherwise in the mock TFLs attached to this SAP.

3.1 Date Coding and Day Numbering

The format for presentation of date variables will be DDMMYYYY. The format for presentation of time variables will be hh:mm.

If dates needed for calculations are only partially given, they will be completed, if meaningful, as follows below:

For the partial start date of an Adverse Event:

- If only the month and/or year of the start date are known, then the adverse event is assumed to have started at the first day of the month/year

For the partial stop date of an Adverse Event known to not be ongoing:

- If only the month and/or year of the stop date are known, then the adverse event is assumed to have ended at the last day of the month/year

Dates with missing years will only be imputed if the correct year is obvious. Deviations will be documented and explained.

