9.6.2. Safety Analyses

No inferential statistical analyses will be performed on the safety data from this study. The Safety Population will be used for all summaries of safety data. Only observed case data will be used. The summarization of AEs will include treatment-emergent AEs (TEAEs; defined as AEs that begin or worsen after the first dose of study drug). TEAEs and treatment-emergent SAEs (TESAEs) will be summarized by MedDRA system organ class (SOC) and preferred term (PT), severity, and relationship to study drug, overall, by nevanimibe HCl dose, and by cohort. Deaths and discontinuations due to AEs will each be summarized, overall, by nevanimibe HCl dose, and by cohort. Clinical safety laboratory results, PE findings, vital signs, and ECG readings will be summarized by value and by change from baseline in the value, where appropriate, for each time point, overall, by nevanimibe HCl dose, and by cohort using summary statistics for continuous parameters, including number of non-missing observations (n), mean and/or median, standard deviation (SD) and/or percentiles, minimum (min), and maximum (max). Frequencies and percentages as well as shift tables will be prepared for categorical parameters.

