3.2.4 Identification of Prior and Concomitant Medications

Identification of prior and concomitant medications will be done by comparison of the start and stop dates of the medication with the date of first dose of study drug.

- **Prior medications:** If the start date is before date of first dose of study drug, the medication is considered to be a prior medication. If the start date is partially given and unambiguously before start of treatment, the medication is also considered to be a prior medication.
- **Concomitant medications:** If the stop date is the same as or after the date of first dose of study drug or the medication is ongoing, the medication is considered to be a concomitant medication. If the stop date is partially given and not unambiguously before the date of first dose of study drug, the medication is considered to be a concomitant medication. If the stop date is missing and the medication is not known to be ongoing, the medication is considered to be a concomitant medication.

4. Analysis Populations and Subgroups

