7.3 Calculation of Study Days and Durations

Study days and, if applicable and meaningful, durations will be determined by comparing the respective date to the date of first dose of study drug.

- If the respective date is on or after date of first dose of study drug:
$$\text{Study day/Duration} = (\text{Date (e.g., date of visit)} - \text{Date of first dose of study drug}) + 1$$
- If the respective date precedes the date of first dose of study drug:

Study day/Duration = Date (e.g., date of medical history event) - Date of first dose of study drug

Time to onset and duration of adverse events will be calculated as follows:

- Time to onset = start date of AE - date of first dose of study drug [+1 for AE starting on or after date of first dose of study drug]
- Duration of adverse event = (stop date - start date) + 1

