7.7 Evaluation of Safety Endpoints

All safety variables will be evaluated for the safety population (SP). The analyses of treatment-emergent adverse events (TEAEs) will be performed overall and for subjects enrolled under global

amendment 1 and global amendment 2 separately. The analysis on the SOC and PT level will be repeated for the All Screened population to cover all AEs, also those recorded prior to first treatment with the study drug.

Treatment-emergent adverse events (TEAEs) will be summarized overall and by causal relationship and severity. TEAEs will be coded using the latest MedDRA version at the time of database close. Incidences and percentages will be provided on the subject-level (n), overall as well as on the system organ class (SOC) level and on the preferred term (PT) level for all subjects and by nevanimibe dose category. Results will additionally be prepared by time range. The suitable time ranges will be selected during the DRM for Cohort 1. A subject with more than one AE overall or assigned to one SOC or assigned to one PT will be counted once for the worst category (causal relationship or severity) on the subject level. For the summarization by relationship to study drug, the relationship will be categorized as “related” and “not related,” where related AEs are those with at least a possible relationship to the study treatment. For the summarization by nevanimibe dose, subjects with more than one AE overall or assigned to one SOC or assigned to one PT will be counted once on the subject level at the lowest nevanimibe dose category on which they experience the AE (i.e., a subject with two AEs, one when treated with 1000 mg BID and one when treated with 1500 mg BID, will be counted once at the 1000 mg BID dose). Additionally, the number of AEs per patient-year of treatment will be calculated by nevanimibe dose as (sum of number of AEs of subjects at the respective nevanimibe dose) / (patient-years of treatment at the respective nevanimibe dose).

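### Partial adverse event start dates are set to the first of the month or year without checking the first-dose date, so on-treatment events can drop out of the TEAE tables

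*SAP*

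**What the plan says.** SAP 3.1 introduces its date rules with "If dates needed for calculations are only partially given, they will be completed, if meaningful, as follows below". For a start date with only the month and/or year known, "then the adverse event is assumed to have started at the first day of the month/year". The only stated exception concerns a missing year: "Dates with missing years will only be imputed if the correct year is obvious". Deviations are to be documented and explained. The rule does not mention the date of first dose.

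The SAP text has no definition of a treatment-emergent event. Protocol 9.6.2 supplies it: "defined as AEs that begin or worsen after the first dose of study drug". SAP 7.3 computes onset from the start date, "Time to onset = start date of AE - date of first dose of study drug", adding 1 for events that start on or after the first-dose date.

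For medications, SAP 3.2.4 does compare partial dates with the start of treatment: "If the start date is partially given and unambiguously before start of treatment, the medication is also considered to be a prior medication". A partial stop date that is not clearly before first dose makes the medication concomitant.

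SAP 7.7 builds its adverse event summaries on treatment-emergent events. It repeats the SOC and PT analysis in the All Screened population to cover all events, "also those recorded prior to first treatment with the study drug".

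**The concern.** Completing a start date to the first of the month is harmless when that day falls on or after first dose, or when the event really began before dosing. It gives a wrong result when the event began on drug in the calendar month of first dose (or in the calendar year of first dose, for a year-only record). The completed date then precedes dosing and the event no longer meets the TEAE definition.

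Such an event leaves the TEAE tables by dose, severity, relationship and time range, and the listings of treatment-emergent SAEs, discontinuations and deaths in SAP Appendix 1. It remains in the All Screened SOC/PT table and the adverse event listing, but neither reports treatment-emergent incidence.

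A first-of-month rule can move an on-treatment onset to before dosing. It can never move a pre-dose onset to after dosing. Any error therefore understates TEAE incidence, and for month-only dates it falls on the first days on drug. Safety is part of the primary objective (protocol 2.1, SAP 2.4.1).

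**Working it through.** The documents give no figure on this point, so there is none to reproduce. The check applies the stated rules to an example and then counts how often they misplace an event.

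**Inputs**
- Completion rule: first day of the known month or year (SAP 3.1).
- TEAE status: onset or worsening after first dose (protocol 9.6.2).
- Study day: date minus first-dose date, plus 1 if on or after first dose (SAP 7.3).
- Treatment length: 16 weeks = 112 days under Amendment 2, 12 weeks = 84 days under Amendment 1 (SAP 2.1).
- Assumptions, not in the documents: first-dose dates spread evenly over a 365-day year, and onset uniform over the treatment days.

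**Example.** First dose 15 September, true onset 20 September, which is 20 − 15 + 1 = Day 6.
- Month only recorded: completed to 1 September; 1 − 15 = Day −14, not treatment-emergent.
- Year only recorded: completed to 1 January, Day −257, not treatment-emergent.

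**Month-only dates**
1. A first dose on day d > 1 of a month with M days puts M − d + 1 on-treatment days before dosing. A first dose on the 1st moves none, so 365 − 12 = 353 of 365 first-dose dates are affected.
2. The sum over one month is M(M − 1)/2: 465 for 31 days, 435 for 30 days, 378 for 28 days.
3. Over the year: 7 × 465 + 4 × 435 + 378 = 5373.
4. Average: 5373/365 = 14.72 days.
5. Share of the treatment period: 14.72/112 = 13.1%; 14.72/84 = 17.5%.

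**Early clustering (assumption).** If onset is 2 or 3 times as frequent in days 1 to 28 as later, the share of 112 days becomes 21.0% or 26.2%.

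**Year-only dates**
1. A first dose on day 2 to 365 of the year moves the smaller of T and the days left in the year, where T is the treatment length.
2. The sum is 34552 for T = 112 and 27090 for T = 84.
3. Averages: 34552/365 = 94.7 days (84.5% of 112) and 27090/365 = 74.2 days (88.4% of 84).

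**Weight of one event.** With 20 to 24 subjects, one subject moved out of a TEAE row changes it by 1/24 = 4.2 to 1/20 = 5.0 percentage points.

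All percentages are conditional on the start date being that incomplete. The documents do not give the number of partial dates, so no absolute count follows.

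**The case against.** The best counter-argument is that SAP 3.1 completes dates only for calculations and only where meaningful, that it documents deviations, and that no sentence says the TEAE flag uses the completed date. On that view the SAP is silent rather than wrong. This does not rescue the rule. A TEAE flag needs a date, the completed date is the only one the SAP supplies, and the qualifier carries no criterion that refers to first dose. It is also true that an event dated too early but worsening on drug stays treatment-emergent under the protocol definition. That helps only events with recorded worsening.

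The second argument is that conduct makes the trigger rare. Subjects are contacted about every two weeks, SAEs are entered within 24 hours of knowledge, and queries and data review meetings precede lock. This stands as to frequency and is why the effect is probably small. It is not a safeguard in itself. Adverse events are collected from consent (protocol 6.10.1), so a pre-dose date is a valid value that a plausibility check need not question.

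Third, TEAEs can also arise after the last dose, during follow-up. Taken over about 143 days (Day 113 plus 30) or 115 days (Day 85 plus 30), the month-only share is 14.72/143 = 10.3% or 14.72/115 = 12.8%. That is the right figure for all TEAEs. The 13.1% and 17.5% refer to events with onset during treatment. The conclusion is the same on either base.

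Finally, the safety summaries are descriptive and ongoing safety oversight does not depend on these tables. Both points are correct and limit the consequence. They do not make the tabulated incidence right.

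**Conclusion.** The concern holds. Read as written, the SAP dates an on-treatment event before dosing whenever its start is known only to the month of a first dose not given on the 1st. The same happens when the start is known only to the year of a first dose not given on 1 January. The error can only lower TEAE incidence.

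Conditional on a month-only date, about 1.3 (112 days) to 1.8 (84 days) of every 10 on-treatment events would be lost. This assumes evenly spread first-dose dates and uniform onset; the share rises if events cluster early. Year-only dates would lose most on-treatment events but should be rare.

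The overall effect is probably small, because few partial dates are expected and the summaries are exploratory. The 40% response criterion is unaffected. True pre-dose events with partial dates are classified correctly and are not part of the finding. The correction should be made because it is cheap and the SAP already makes the comparison for medications.

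**What to change.** Amend SAP 3.1 along these lines: if the known month and year (or year alone) of the adverse event start equals that of first dose, and neither the stop date nor another record shows onset before dosing, impute the date of first dose and class the event as treatment-emergent; otherwise impute the first day of the month or year. Add that the TEAE flag and time to onset both use this imputed date, and put the TEAE definition itself in the SAP.

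In the example, the onset moves from Day −14 (month only) or Day −257 (year only) to Day 1, and the event is counted.

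The cost is one or two sentences and one program line before database lock. The downside is that a few true pre-dose events may be counted as treatment-emergent. That is the conservative direction and matches how SAP 3.2.4 resolves ambiguous medication dates. Setting the rule before lock also avoids case-by-case decisions by a sponsor who can see the open-label data.
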